### Table 75: DPOAE Measurement and Change from Baseline by Timepoint, Frequency, and Ear – Safety Population

Table with similar format:

 Table 76:
 DPOAE Measurement and Change from Baseline by Timepoint, Frequency, and Ear – Safety Subset Population
				DPOAE Result						
		Frequency		Pr	esent	Ab	sent			
Ear	Timepoint	(kHz)	Ν	n	%	n	%			
Right	Baseline	1.5	х	х	XX	х	xx			
		2.0	х	х	XX	х	xx			
		3.0	х	х	XX	х	xx			
		4.0	х	х	XX	х	xx			
		6.0	х	х	XX	х	xx			
	Day 3	1.5	х	х	XX	х	xx			
			х	х	XX	х	xx			
	Day 14	1.5	х	х	XX	х	xx			
			х	х	XX	х	xx			
	Day 30	1.5	х	х	XX	х	xx			
			х	х	XX	х	xx			
Left	Baseline	1,5	х	х	XX	х	xx			
			х	х	XX	х	xx			
Notes: N = Nu Baseline = The	mber of participants in the Safety	y Subset Population wi	th the DPAO	Es assessed at t	he respective tim	epoint and freq	uency.			

 Table 77:
 Summary of DPOAE Results by Timepoint, Frequency, and Ear – Safety Population

Table with similar format:

### Table 78:Summary of DPOAE Results by Timepoint, Frequency, and Ear – Safety Subset
Population

					Measu	rement			Change from	Baseline (dB)	
Ear	Timepoint	Frequency (kHz)	Ν	Mean	SD	Median	Min, Max	Mean	SD	Median	Min, Max
Right	Baseline	1.5	х	XX.X	XX.X	XX.X	xx, xx	-	-	-	-
		2.0	Х	XX.X	XX.X	XX.X	XX, XX	-	-	-	-
		3.0	Х	XX.X	XX.X	XX.X	XX, XX	-	-	-	-
		4.0	х	XX.X	XX.X	XX.X	XX, XX	-	-	-	-
		6.0	х	XX.X	XX.X	XX.X	XX, XX	-	-	-	-
	Day 3	1.5	х	XX.X	XX.X	XX.X	XX, XX	XX.X	XX.X	XX.X	xx, xx
			х	XX.X	XX.X	XX.X	xx, xx	XX.X	XX.X	XX.X	xx, xx
	Day 14	1.5	х	XX.X	XX.X	XX.X	XX, XX	XX.X	XX.X	XX.X	xx, xx
			х	XX.X	XX.X	XX.X	XX, XX	XX.X	XX.X	XX.X	xx, xx
	Day 30	1.5	х	XX.X	XX.X	XX.X	XX, XX	XX.X	XX.X	XX.X	xx, xx
			х	XX.X	XX.X	XX.X	xx, xx	XX.X	XX.X	XX.X	xx, xx
Left	Baseline	1.5	х	XX.X	XX.X	XX.X	xx, xx	-	-	-	-
			х	XX.X	XX.X	XX.X	xx, xx	-	-	-	-
Notes: N = Nur	nber of participants in the Saf	ety Population with the	DPAOEs asso	essed at the resp	pective timepoi	nt and frequend	cy. Baseline = T	he most recent	measurement p	rior to start of	infusion.

#### Table 79: SNR Change from Baseline by Timepoint, Frequency, and Ear – Safety Population

Table with similar format:

 Table 80:
 SNR Change from Baseline by Timepoint, Frequency, and Ear – Safety Subset Population

#### 14.4 Summary of Concomitant Medications

#### Table 81: Number and Percentage of Participants with Prior Medications by WHO Drug Classification and Cohort – Safety Population

[Implementation Note: Include prior medications (medications with an end date prior to date of infusion) only.]

WHO Drug Code	WHO Drug Code	Coh (N=	ort 1 =X)	Coh (N	ort 2 =X)	Coh (N=	ort 3 =X)	Coh (N	ort 4 =X)	Cohort 5 (N=X)		All Participants (N=X)	
Level 1, Anatomic Group	Level 2, Therapeutic Subgroup	n	%	n	%	n	%	n	%	n	%	rt 5 All Parti X) (N= % n xx x 	%
Any Level 1 Codes	Any Level 2 Codes	х	xx	х	xx	х	xx	х	XX	х	xx	x	XX
[ATC Level 1 - 1]	Any [ATC 1 – 1]												
	[ATC 2 - 1]												
	[ATC 2 - 2]												
	[ATC 2 - 3]												
[ATC Level 1 – 2]	[ATC 2 - 1]												
	[ATC 2 - 2]												
	[ATC 2 - 3]											1	
Notes: N = Number of participant	s in the Safety Population. $n =$ Number of	f participar	nts reportin	g taking at	least one i	medication	in the spec	ific WHO	Drug Class	5.			

### Table 82:Number and Percentage of Participants with Concomitant Medications by WHO Drug Classification and Cohort – Safety
Population

WHO Drug Code	WHO Drug Code	Coh (N=	ort 1 =X)	Coh (N=	ort 2 =X)	Coh (N=	ort 3 =X)	Coh (N	Cohort 4 (N=X)		Cohort 5 (N=X)		All Participants (N=X)	
Level 1, Anatomic Group	Level 2, Therapeutic Subgroup	n	%	n	%	n	%	n	%	n	%	n	%	
Any Level 1 Codes	Any Level 2 Codes	х	xx	х	xx	х	xx	х	xx	х	xx	х	xx	
[ATC Level 1 - 1]	Any [ATC 1 – 1]													
	[ATC 2 - 1]													
	[ATC 2 - 2]													
	[ATC 2 - 3]													
[ATC Level 1 – 2]	[ATC 2 - 1]													
	[ATC 2 - 2]													
	[ATC 2 - 3]													
Notes: N = Number of participants	in the Safety Population. n = Number of	f participar	nts reportin	g taking at	least one n	nedication	in the spec	ific WHO	Drug Class	5.	•	•	•	

[Implementation Note: Include concomitant medications (medications that are ongoing or have an end date after date of infusion) only.]

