## 8.3 Bronchoscopy with Bronchoalveolar Lavage

Bronchoscopy with bronchoalveolar lavage is performed to obtain fluid samples from a lung segment following dosing with apramycin to measure the accumulation of the drug in the lung. The procedure will be performed in the Pulmonology Department of the UTMC, which is accredited to perform this procedure, according to established SOPs by licensed and experienced

pulmonologists and support staff. The procedure will be done in eligible and enrolled subjects who were assigned to cohorts T1-T5, at the following nominal timepoints:  $0.5 \text{ h} \pm 5 \text{ min}$  (T1), 2h  $\pm 5 \text{ min}$  (T2), 4 h  $\pm 10 \text{ min}$  (T3), 8 h  $\pm 15 \text{ min}$  (T4) and 24 h (nominal)  $\pm 1$  h (T5) after the start of apramycin infusion. (The exact timing of T5 will be determined after review of BAL apramycin concentrations in cohorts T1 to T4.) Subjects in each cohort will have only one procedure done during the study.

Subjects, who had previously been informed of the procedure and provided informed consent, will be taken to the bronchoscopy suites by CTU staff, will review the procedure with the operator and confirm understanding prior to the procedure. The subject will be monitored during the procedure by VS, pulse oximetry and will receive oxygen as needed. Sedation or light anesthesia will be induced by appropriate intravenous medications. The procedure will be performed according to standard protocol and a study-specific protocol (SSP) for the collection of BAL samples for PK analysis. BAL samples will be stored on ice and then transferred into test tubes to the CTU research lab for measurement of total and differential cell counts and for centrifugation and processing into BAL supernatant (containing ELF) and BAL pellet (containing AM) samples. After the procedure, the subject will be observed in the recovery room for side effects and will be released by the pulmonologist to the care of the CTU staff when stable. The subject will continue to be monitored closely until discharge from the CTU. Procedure records will be obtained by the CTU staff.

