# 4. INVESTIGATIONAL PLAN

# 4.1. Overall Study Design and Plan

This is a Phase 1, single center, open-label study to evaluate the plasma and lung PK, safety and tolerability of a single IV dose of apramycin in 20 healthy male and female participants 18 to 45 years of age (inclusive). Each participant will be enrolled into one of five cohorts (T1-T5) before dosing on Day 1. Four participants will be allocated to each cohort. Each cohort corresponds to a timepoint after dosing when a single bronchoscopy with BAL will be performed: 0.5 h ( $\pm$  5 min) (Cohort T1), 2 h ( $\pm$  5 min) (Cohort T2), 4 h ( $\pm$  10 min) (Cohort T3), 8 h ( $\pm$  15 min) (Cohort T4), and 24 ( $\pm$  1 h) (Cohort T5). The timing of bronchoscopy and BAL in Cohort T5 is nominal. The final timepoint will be determined after analysis of apramycin concentrations in BAL in Cohorts T1-T4. If apramycin is detectable in BAL from Cohorts T1-T4, then T5 will be enrolled. If it is not detectable, then Cohort T5 will not be enrolled.

A diagram of the overall study design is shown in Figure 1. Participants will participate in the study for approximately 58 days, including a 28-day screening period, consisting of an out-patient period of 26 days (Day -28 to Day -3) with 1 to 2 site visits and 2 in-patient days; Day -2 and Day -1, to confirm eligibility for admission (Day -2) and eligibility for enrollment (Day -1), complete baseline assessments for ENT and otoacoustic tests (Day -2), and complete time-matched ECGs (Day -1); a 3-day in-patient treatment period, to confirm eligibility for dosing (Day 1), complete baseline VS, clinical labs, and exploratory labs before dosing (Day 1), administer treatment (Day 1), perform bronchoscopy with BAL within 24 hours after dosing (timepoints T1-T4 on Day 1 and T5 on Day 2), and complete in-patient follow up on Days 2 and 3; and a 27-day out-patient follow-up period to complete site visits on Day 14 ( $\pm$  3 days) and Day 30 ( $\pm$  4 days), the last follow-up visit. It is anticipated that the duration of the study will be about 6 months to enroll Cohort T1-T4 and 10 months to complete Cohort T5, if enrolled, following an interim data analysis to review lung PK data.

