#### 4.4.7. **Prior and Concomitant Therapy**

Medications include the following: prescription drugs, birth control hormonal preparations, non-prescription medication, herbs, vitamins, nutritional supplements, and illicit and recreational substances.

Medications taken before or after dosing will be reported as Prior Medications or Concomitant Medications (ConMeds), respectively.

**Prior prescription medications** will be recorded at Screening Visit. All prior medications are not allowed during the study period with the exception of oral contraceptives, which are permitted throughout the study, and solitary doses of up to 1,000 mg acetaminophen (paracetamol).

The following medications are prohibited for the indicated periods prior to dosing:

- Use of any investigational drug product within 30 days or 5 half-lives (whichever is longer) before dosing or planned use during the study period (screening until Final Visit).
- Use of aminoglycosides within 3 months prior to dosing.
- Use of neuromuscular blocking agents within 1 week or 5 half-lives (whichever is longer) prior to dosing.
- Use of potentially nephrotoxic medication 2 weeks prior to dosing: Renin– angiotensin-aldosterone system inhibitors: angiotensin-converting enzyme-inhibitors, angiotensin II-receptor antagonists (enalapril, lisinopril, ramipril captopril, benazepril), spironolactone, eplerenone; non-steroidal anti-inflammatory drugs (aspirin, ibuprofen, naproxen, indomethacin, etc.) including cyclooxygenase 2 selective inhibitors (Bextra, Celebrex, Vioxx).
- Use of potentially ototoxic medication 3 months prior to dosing: vancomycin, loop diuretics (bumetanide, ethacrynic acid, furosemide), quinine and quinidine derivatives including mefloquine with the exception of occasional intake of quinine containing beverages.

**Non-prescription medications, herbs, vitamins, and nutritional supplements** will not be taken within 15 days before dosing and during the trial. *Exceptions*: vitamins and over the counter (OTC) medications taken for < 48 h for the treatment of common symptoms (e.g., headache, indigestion, muscle pain) may be allowed if approved by the designated study clinician.

**Blood/blood products** (red blood cells [RBCs], white blood cells [WBCs], platelets, and plasma) donation of 500 mL within 3 months or more than 100 mL within 30 days before signing informed consent to this trial is not allowed, and it is prohibited during the course of this trial.

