Following dosing, each new ConMed and changes to existing medications will be recorded. Participants will be required not to utilize non-study medications during the trial except those deemed necessary by the Site PI or sub-investigator.

Any drug (e.g., non-prescription medications, herbal supplements, vitamins, or prescription medications) or vaccines or blood/blood products used by the participant during the trial will be recorded in the participant's source documents and on the appropriate electronic case report form (eCRF), and the PI or authorized study clinician (listed on FDA Form 1572) will note whether the use was medically indicated and immediately necessary. Any use of medications not authorized by the study PI or authorized clinician will be recorded as a deviation.

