### 9.1.2. Prior and Concomitant Medications

All medications will be coded to the Anatomical Therapeutic Classification (ATC) using the current version of the WHO Drug Dictionary. The use of prior and concomitant medications taken during the study will be summarized by ATC 1 and ATC 2 (separately, in Table 81 for prior medications and Table 82 for ConMeds). Individual participant listings will be presented for all prior and concomitant medications (separately in Listing 27 for prior medications and Listing 28 for ConMeds).

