#### 16.2.12 Concomitant Medications

### Listing 27: Prior Medications

[Implementation Note: Include prior medications (medications with an end date prior to dosing) only. If start date is more than 30 days before enrollment, then categorize as follows:

- 5 years prior to enrollment
- 1-5 years prior to enrollment
- 1-12 months prior to enrollment

If taken for MH, display "Yes" with the MH Number in parentheses, e.g., "Yes (7)". Sort order: Cohort, Participant ID, and CM Number.]

Cohort	Participant ID	CM Number	Medication	Medication Start Day	Medication End Day	Indication	Taken for a condition on Medical History? (MH Description; Number)	ATC Level 1 (ATC Level 2)

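### A drug given after dosing and stopped on the infusion date appears in none of the SAP's four medication outputs (Tables 81-82, Listings 27-28)

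*SAP*

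**What the plan says.** The body of the SAP draws the line at dosing. Section 4.4.7 (Prior and Concomitant Therapy) states: "Medications taken before or after dosing will be reported as Prior Medications or Concomitant Medications (ConMeds), respectively". It also requires that any drug used during the trial "will be recorded in the participant's source documents and on the appropriate electronic case report form (eCRF"). Section 9.1.2 adds: "Individual participant listings will be presented for all prior and concomitant medications".

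The shells use end-date filters instead:

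- Table 81 (prior): "Include prior medications (medications with an end date prior to date of infusion) only".
- Listing 27 (prior): "Include prior medications (medications with an end date prior to dosing) only".
- Table 82 and Listing 28 (concomitant), with identical wording: "Include concomitant medications (medications that are ongoing or have an end date after date of infusion) only".

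On the timing of the procedure, SAP 4.1 plans to "perform bronchoscopy with BAL within 24 hours after dosing (timepoints T1-T4 on Day 1 and T5 on Day 2"). Protocol 8.3 says of the procedure: "Sedation or light anesthesia will be induced by appropriate intravenous medications".

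**The concern.** The two concomitant shells need a stop date later than the infusion date, or no stop date. The two prior shells need a stop before the infusion date or before dosing. Nothing covers a stop on the infusion date itself for a drug given after dosing. Each note ends with the word only, so a programmer who follows the shells would drop such a record from tables and listings alike.

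Three things are at stake. Listing 28 holds the columns that tie a medication to an adverse event and record whether a study clinician authorized it; both are lost for same-day drugs. The listings would not deliver the completeness promised in 9.1.2. And Table 82 is laid out by cohort, while the day of bronchoscopy differs by cohort, so the gap could act unequally on sedation drugs.

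**Working it through.** **Inputs.** Let D be the infusion date. The rules come from the notes to SAP Tables 81 and 82 and Listings 27 and 28. BAL times are 0.5, 2, 4, 8 and a nominal 24 h after the start of infusion for T1 to T5 (SAP 4.1). SAP section 5 plans 5 cohorts of 4, and 5 × 4 = 20 reproduces its total. T1-T4 is 4 × 4 = 16, and T5 is 4.

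**Step 1: apply the four rules.**

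| Medication | Table 81: end date < D | Listing 27: ended before dosing | Table 82 and Listing 28: ongoing or end date > D |
|---|---|---|---|
| Given after dosing, stopped on D | no | no | **no** |
| Given after dosing on D, stopped on D+1 | no | no | yes |
| Given after dosing on D, ongoing | no | no | yes |
| Stopped on D before dosing | no | yes, if clock times are used | no |

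The first row appears in 0 of 4 outputs. The word ongoing does not rescue it: Listing 28 uses it as the entry in the end-day column, so it means that there is no stop date. The last row shows a smaller mismatch, because Table 81 and Listing 27 use different cut-offs for the same category.

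**Step 2: same-day treatment of an adverse event.** All five cohorts are dosed on Day 1. A drug given after dosing and stopped that day has end date = D whatever the cohort, so it is lost in all five, T5 included. A Day 1 drug that runs into Day 2 is kept in all five.

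**Step 3: sedation, if entered as a concomitant medication.**

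- T1-T4: the procedure is on Day 1. If sedation ends that day, end date = D and 0 of 16 appear.
- T5 at its nominal 24 h: the procedure is on Day 2, so end date = D+1 and 4 of 4 appear.
- Total shown: 4 of 20. If T5 is not enrolled, 0 of 16.

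**Step 4: sensitivity to dosing time.** T4 is the only T1-T4 cohort at realistic risk of crossing midnight. Assume sedation ends 30 min after the 8 h timepoint (the documents give no duration). It stays on D if the start of infusion + 8 h + 0.5 h falls before 24:00, that is, for dosing before 15:30. With later dosing (checked at 15:30 and 16:00) T4 is captured, so 3 × 4 = 12 are lost and 20 − 12 = 8 are shown.

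**Step 5: under the amended rule.** With concomitant defined as ongoing, or stopped at or after the start of infusion, sedation is captured for 16 + 4 = 20 of 20. Post-dose drugs stopped on Day 1 are captured in every cohort.

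**The case against.** The strongest reply is that the SAP body already states the right rule and that the shells are only loosely worded. The first half is true, and it makes this an inconsistency between shells and body rather than a disputed choice of analysis. It does not remove the problem, because the shells are the programming instruction and their wording is explicit.

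The second reply concerns sedation, and it stands as a limit on the 16-of-20 figure. The schedule (Protocol Appendix A; SAP Table 2) gives sedative or anesthetic administration its own row, apart from concomitant medication. Protocol 7.5.1 leaves to the MOP which procedure-record data reach the CRF. SAP 4.4.7 requires an appropriate eCRF but does not name the form. If sedation sits on a procedure form, it is in the medication tables for no cohort, and the contrast with T5 does not arise.

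A reader might also infer more than the documents support:

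- *That Day 1 treatments of adverse events would show only for T5.* T5 is dosed on Day 1 too, so its same-day drugs are lost as well. In every cohort, drugs that continue into Day 2 are kept. The contrast between cohorts can concern sedation only.
- *That Day 1 safety data could not be interpreted.* In T3 the 4 h ECG and vital signs precede sedation by rule (Protocol 7.5.1), and in T4 the scheduled 1 h and 4 h readings come before the 8 h procedure. The nominal time of sedation is known from the cohort. Listing 8 and Tables 21-22 carry an alternative-etiology column.
- *That the requirement to record all drugs is breached.* Collection is untouched; only reporting is affected.

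**Conclusion.** The gap is certain on the wording: a post-dose drug with a stop date equal to the infusion date is left out of all four outputs, contrary to SAP 4.4.7 and 9.1.2. For same-day treatment of adverse events it applies in all five cohorts, up to the planned 20 participants. The documents give no expected number of such drugs.

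The sedation figure is conditional: 16 of 20 planned participants lost and 4 shown, with a false contrast between cohorts in Table 82. It assumes that sedation is entered as a concomitant medication, that it ends on the infusion date in T1-T4, and that T5 stays on Day 2 (its 24 h time is nominal). It counts planned participants, before any replacements.

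This is an error of safety reporting that should be corrected before the outputs are produced. It does not touch the primary PK endpoints, and no PK or adverse-event summary is derived from Table 82.

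**What to change.** Put one rule in the notes to Tables 81 and 82 and Listings 27 and 28:

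- Prior: stopped before the start of infusion.
- Concomitant: ongoing, or stopped at or after the start of infusion.
- Where only a date is recorded and it equals the infusion date: concomitant.

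The date-only clause is needed because the listing shells show start and end days, not clock times. Its price is small: a drug stopped before dosing that day, with no recorded time, is counted as concomitant. A separate row for sedation is not needed to close the gap.

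The cost is four shell notes and the matching filter in the program, with no new data collection where stop dates are recorded. SAP section 15 allows an addendum before final data lock. It would also help to state in the SAP whether sedation drugs are on the concomitant medication form, so that a reader of Table 82 knows whether to expect them.

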#### 14.2 Pharmacokinetics Data

#### Table 83: Total Apramycin Concentrations in Plasma

[Implementation Note: Mark concentrations collected out of window with an asterisk (\*) next to the concentration and include a footnote: "Samples collected out of window are noted by an asterisk (\*)". Mark concentrations collected substantially out of window with two asterisks (\*\*) next to the concentration and include a footnote: "Samples collected substantially out of window are noted by two asterisks (\*\*)". Mark imputed concentration times with three asterisks (\*\*\*) next to the concentration and include a footnote: "Samples collected substantially out of window are noted by two asterisks (\*\*\*)". Mark imputed concentration times with three asterisks (\*\*\*) next to the concentration and include a footnote: "Samples with imputed collection times are noted by three asterisks (\*\*\*)".]

					Ň	lominal Time a (l	n)				
Participant ID	0	0.5	1	2	4	8	16	24	36	48	60
PH2.00123	Х	х	х	х	х	х	х	Х	х	х	Х
PH2.00124	х	х	х	х	х	х	х	Х	х	х	Х
PH2.00125	х	х	х	х	Х	х	Х	Х	х	Х	Х
Statistics	х	х	х	х	Х	х	Х	Х	х	Х	Х
N b	х	х	х	х	Х	х	Х	Х	х	Х	Х
Mean	х	х	х	х	Х	х	Х	Х	х	Х	Х
SD	х	х	х	х	Х	х	Х	Х	х	Х	Х
GM	х	х	х	х	Х	х	Х	Х	х	Х	Х
CV%	х	х	х	х	Х	х	Х	Х	х	Х	Х
Min	Х	Х	Х	X	Х	X	Х	Х	Х	Х	X
Max	Х	X	х	х	х	х	х	х	х	х	Х

Notes: Concentrations are reported in units of  $\mu$ g/ml.

[Out of window footnotes here, if applicable]

a Times are relative to time of dosing.

b Number of data points used to compute the summary statistics. For calculation of summary statistics, BQL values were imputed as 0 if the sample was taken before the first measurable PK sample with a concentration above the LLOQ. BQL values were treated as missing otherwise.

Table with Similar Format:

#### Table 84: Free Apramycin Concentrations in Plasma

#### Table 85: Summary Statistics for the Free Portion of Plasma Apramycin

			Summary Statistics							
Nominal Time a (h)	Ν	Mean	SD	Median	Min, Max					
0.5	Х	XX.X	XX.X	XX.X	XX, XX					
36	Х	XX.X	XX.X	XX.X	XX, XX					
Note: N = Number of data points used to calculate the summary statistics. Concentrations are reported in units of µg/mL. a Times are relative to time of dosing.										

	e		I V						
Statistics	C max (µg/mL)	T max (h)	AUC(0-24) (μg *h/mL)	AUC (0-last) (μg*h/mL)	AUC (0-∞) (μg*h/mL)	Ke (1/h)	t 1/2 (h)	CL (L/h)	V d (L)
Ν	х	х	х	Х	х	Х	х	х	х
Mean	х	х	х	Х	х	Х	х	х	х
SD	х	х	х	Х	х	Х	х	х	х
Min	х	х	х	X	х	Х	х	х	х
Max	х	х	x	X	х	Х	х	х	х
CV%	х	х	x	X	х	Х	х	х	х
GM	х	х	x	X	х	Х	х	х	Х
Note: $N = Number of d$	Note: N = Number of data points used to compute the summary statistics.								

#### Table 86: Summary Statistics for Total Apramycin in Plasma PK Parameters

Table 87:	Summary Statistics for Apramycin in ELF Concentrations and Apramycin in ELF to Total Apramycin in Plasma Concentration
	Ratios

	Total Apramycin in Plasma Concentration (μg/mL)					Apramycin in ELF Concentration (µg/mL)					Conce	ntration Ra Apra	tio Apramyo amycin in Pl	cin in ELF to Total Plasma			
Statistics	0.5 h	2 h	4 h	8 h	24 h	0.5 h	2 h	4 h	8 h	24 h	0.5 h	2 h	4 h	8 h	24 h		
Ν	х	х	х	х	х	х	х	х	х	х	х	х	х	х	x		
Mean	х	х	х	х	х	х	х	х	х	х	х	х	х	х	х		
SD	х	х	х	х	х	х	х	х	х	х	х	х	х	х	х		
Min	х	х	х	х	х	х	х	х	х	x	х	х	х	х	х		
Max	х	х	х	х	х	х	х	х	х	x	х	х	х	х	х		
CV%	х	х	х	х	х	х	х	х	х	x	х	х	х	х	х		
GM	х	х	х	х	х	x	х	х	х	x	х	х	х	х	x		
Note: N = Num	ote: N = Number of data points used to compute the summary statistics.																

Tables with Similar Format:

Table 88:Summary Statistics for Apramycin in AM Concentrations and Apramycin in AM to Total Apramycin in Plasma Concentration
Ratios

